5.3 STUDY DEVICE

The study device is the OMNI Plus Surgical System. Subjects randomized to one of the two OMNI treatment groups will undergo either ab-interno transluminal viscoelastic delivery for both hemispheres (360 degree treatment must be attempted) and trabeculotomy for one hemisphere (360 degree treatment must be attempted) (OMNI group), or to canaloplasty only (360 degree treatment must be attempted).

The Comparator group is:

- iStent inject (original or “W”)

5.4 STUDY SITES

Study sites and surgeons will be selected based on experience and necessary resources to conduct clinical research and surgeon experience with the iStent inject and other MIGS.

This study will be conducted at up to 24 sites in the European Union, the United Kingdom, and/or Switzerland.

6 STUDY ENDPOINTS

6.1 EFFECTIVENESS ENDPOINTS

The Primary effectiveness endpoint is:

Mean change in **unmedicated** DIOP from baseline at the 12-month postoperative examination

Other effectiveness endpoints are:

- Proportion of eyes with unmedicated mean DIOP between 6 and 18 mmHg inclusive at the 12-month postoperative examination
- Proportion of eyes with a $\geq 20\%$ decrease in unmedicated mean diurnal IOP (DIOP) at the 12-month postoperative examination
- Mean change in the number of ocular hypotensive medications at the 12-month postoperative visit compared to Screening
- Percent change in unmedicated DIOP from baseline to 12 months
Change in Ocular Surface Disease Index (OSDI) and Glaucoma Quality of Life (GQL-15) scores from screening at 12 months.

6.2 SAFETY ENDPOINTS

- Rates of ocular adverse events (AE) (intraoperative, postoperative)
- Reduction in best corrected distance visual acuity (BCDVA) from screening
- Secondary Ocular Surgical Interventions, including laser, for IOP control

7 STUDY SELECTION CRITERIA

7.1 INCLUSION CRITERIA

For inclusion in this study, subjects must meet all the following criteria (only one eye of each subject is eligible, and all ocular criteria apply to the study eye only unless otherwise indicated):

1. Male or female subjects, 18 years or older
2. Pseudophakic. History of uncomplicated cataract surgery and posterior chamber IOL implantation without compromise to the lens capsule, zonular dehiscence/rupture or vitreous prolapse, [REDACTED].
3. Diagnosis of open angle glaucoma (POAG) including pigmentary and pseudoexfoliation substantiated using funduscopic exam (or OCT) and at least one reliable visual field test with the Humphrey automated perimeter using the SITA Standard 24-2 testing algorithm or an Octopus perimeter program G1 or G1X. Mean deviation score must be ≥ -12.0 dB (Humphrey) or ≤ 12.0 dB (Octopus). The visual field test may be historical (within 6 months prior to Screening Visit). If needed, visual field testing may be repeated between the Screening Visit and the Baseline Visit.
4. At the Screening visit, on 1-5 ocular hypotensive medications (fixed combinations counted as number of components) with a medicated IOP of ≤ 33 mmHg.
5. At the Baseline visit, unmedicated DIOP of ≥ 22 mmHg (≥ 24 mmHg for at least one timepoint and no less than 21 mmHg at any time point) and ≤ 36 mmHg and ≥ 3 mmHg higher than the medicated IOP at the Screening visit.
6. Scheduled for ab-interno minimally invasive canal-based glaucoma surgery.
7. Shaffer grade of ≥ 3 in all four quadrants
8. Able and willing to comply with the protocol, including all follow-up visits.
9. Understands and signs the informed consent.

7.2 EXCLUSION CRITERIA

A subject who meets any of the criteria listed below (in the study eye, unless otherwise indicated) will be excluded from the study:

1. Any of the following prior treatments for glaucoma:
 - Suprachoroidal stent [REDACTED]
 - Laser trabeculoplasty \leq 8 weeks prior to Baseline visit
 - Implanted with a MIGS or other glaucoma device [REDACTED]
[REDACTED]
 - Trabeculectomy or other bleb forming procedure [REDACTED]
[REDACTED]
 - Prior canaloplasty, goniotomy, or trabeculotomy [REDACTED]
[REDACTED]
 - Ciliary ablation procedures including Endocyclophotocoagulation (ECP), Cyclophotocoagulation (G probe), or Micropulse laser, or high intensity focused ultrasound (HIFU) \leq 6 months prior to Baseline visit
2. Any other form of glaucoma other than OAG
3. Use of topical ocular steroids that cannot be stopped a [REDACTED]
[REDACTED]
4. In the Investigator's judgement, predisposed to significant risk because of washout of ocular hypotensive medications.
5. Concurrent ocular pathology or systemic medical condition which, in the Investigator's judgment, would either place the subject at increased risk of complications, contraindicate surgery, place the subject at risk of significant vision loss during the study period (e.g., wet AMD, corneal edema, Fuch's dystrophy, active intraocular infection or inflammation within 30 days prior to Screening Visit, etc.), or interfere with compliance to elements of the study protocol (e.g., returning to investigator's office for follow-up visits).
6. History of penetrating keratoplasty or other corneal transplant; corneal abnormality that would prevent reliable IOP measurement (e.g. keratoconus, abnormally thick [\geq 600 μ M] or thin [\leq 500 μ M] cornea based on optical or ultrasound pachymetry of central corneal thickness [CCT])

7. BCDVA of 6/60 (20/200) or worse in the fellow eye not due to cataract
8. Participation of the study eye in any other ocular interventional study ≤ 30 days prior to Baseline visit and throughout this study
9. Women of childbearing potential if they are currently pregnant or intend to become pregnant during the study period; are breast-feeding; or are not in agreement to use adequate birth control methods to prevent pregnancy throughout the study)

8 STUDY PROCEDURES

8.1 PROCEDURES PER STUDY VISIT

[figure not shown]
Procedures required by the protocol to be conducted at each study visit are listed in the Table 1, Study Visit Schedule and detailed in Appendix A, Section 19.1 CLINICAL TRIAL PROCEDURES.

A brief summary of the procedures performed by visit is provided here.

- At Screening, the subject will complete the informed consent process and sign an informed consent document. Standard procedures will be performed to determine subject eligibility. If needed, a second visual field exam may be conducted before surgery to confirm study eligibility. Wash-out of ocular hypotensive medications will commence.
- At Baseline, eligibility will be confirmed including meeting the unmedicated DIOP criteria. Eligible subjects will be randomized to treatment and scheduled for surgery. Ineligible subjects will be exited.
- At Surgery, subjects will either receive canaloplasty and trabeculotomy in the study eye with the OMNI Surgical System, canaloplasty with the OMNI Surgical System or be implanted with the iStent inject.
- At postoperative follow-up (Week 1, Months 1, 3, 6, and 12), safety and effectiveness assessments will be performed.

8.2 SELECTION OF THE STUDY EYE

Only one qualified eye per subject may be treated under the study protocol. If both eyes qualify for the study during screening, the eye with the higher DIOP at the Baseline visit will be designated as the study eye. If the DIOP of both eyes is the same, then the Investigator will determine the study eye.

8.4 STUDY VISITS

8.4.1 SCREENING VISIT

Informed Consent and Point of Enrollment

Informed consent will be obtained in writing from all subjects and the process documented prior to the performance of any procedure specific to the study using the Ethics Committee approved informed consent form. The Investigator or a trained authorized designee will conduct the informed consent process. Subjects will be given ample time to read and understand the informed consent form and to consider participation in the study. Subjects will be given a copy of the signed and dated informed consent form.

After obtaining an understanding of the purpose of this study, then providing written informed consent, all potential subjects will undergo an initial screening examination in order to determine their eligibility for the study. Exams and tests listed in the Screening column of Table 1 should be performed. Refer to Appendix A for instructions for performing the exams.

The Investigator must retain the original, signed written informed consent document.

Eligibility and Study Entry

Below is a list of study procedures to be undertaken at Screening Visit which must take place from 45 days to 6 days before surgery. Data collected at screening are considered baseline data. Conduct ocular assessments in both eyes.

1.	[REDACTED]
	[REDACTED]
	[REDACTED]
	[REDACTED]

Following confirmation of eligibility per study inclusion and exclusion criteria, subjects will be scheduled for the Baseline visit allowing sufficient time for complete washout of ocular hypotensive medication (refer to Table 2). Ineligible subjects must be exited from the study. The reason for ineligibility must be documented for each enrolled subject.

Subjects who are currently taking IOP-lowering medications will undergo the washout procedure described below and in Table 2 before the Baseline visit.

Subject exam data collected prior to enrollment as part of routine patient care may serve as Screening data as long as it was collected within 15 days prior to the visit with the following exceptions:

- IOP and IOP-lowering medications. These data must be collected at the Screening visit.
- Visual fields: A historical visual field may be used IF conducted per the protocol method (Humphrey automated perimeter using the SITA Standard 24-2 testing algorithm or an Octopus perimeter program G1 or G1X.) AND is within 6 months of the Screening visit.

Washout of Hypotensive Medications

Subjects who meet all screening eligibility criteria will be instructed to discontinue their ocular hypotensive medication regimen, and to return for a Baseline visit after completing the appropriate washout period.

All subjects on ocular hypotensive medication(s) at Screening and Month 12 will be instructed to undergo a washout prior to the Baseline or Month 12 postoperative visit, respectively. If the study subject fails to remember to not use ocular hypotensive medication for the study eye per the required washout period, they can be re instructed and restart the washout. If deemed necessary by the PI, a subject can be given hypotensive medications after the baseline visit until the day of surgery. An oral hypotensive medication can be used between baseline to surgery. The minimum washout periods are specified in Table 2 below.

NOTE: A safety IOP check mid-way through the wash-out period may be performed at the Investigator's discretion where warranted to ensure subject safety.

Table 2: Ocular Hypotensive Medication Washout Periods

Brand Name/Chemical Name	Minimum washout period
Carbonic Anhydrase Inhibitors	
Diamox® (Acetazolamide) – oral Rx	5 days
Neptazane® (Methazolamide) – oral Rx	5 days
Azopt® (Brinzolamide)	5 days
Trusopt® (Dorzolamide Hydrochloride)	5 days
Muscarinic Agonists	
Salagen, Pilocar (Pilocarpine)	5 days
Alpha Adrenergic Agonists	
Alphagan® (Brimonidine)	14 days
Iopidine® (Apraclonidine Hydrochloride)	14 days
Beta Blockers	
Betagan® (Levobunolol Hydrochloride)	28 days
Betoptic® (Betaxolol Hydrochloride)	28 days
OptiPranolol® (Metipranolol)	28 days
Timoptic/Betimol® (Timolol Maleate)	28 days
Prostaglandin Analogs	
Lumigan® (Bimatoprost)	28 days
Travatan® (Travoprost)	28 days
Xalatan® (Latanoprost)	28 days
Zioptan® (Tafluprost)	28 days
Vyzulta® (Latanoprostene Bunod)	28 days
Rho Kinase Inhibitor	
Rhopressa® (Netarsudil)	28 days
Fixed Combination Medications	
Combigan® (Brimonidine Tartrate/Timolol Maleate)	28 days
Cosopt® (Dorzolamide Hydrochloride/ Timolol Maleate)	28 days
DuoTrav® (Travoprost/Timolol)	28 days
Ganfort® (Bimatoprost/Timolol)	28 days
Rocklatan® (Netarsudil/Latanoprost)	28 days
Simbrinza® (Brinzolamide/Brimonidine Tartrate)	28 days
Xalacom® (Latanoprost/Timolol)	28 days
Krytantek (Brimonidine Tartrate/ Dorzolamide Hydrochloride/ Timolol Maleate)	28 days
Other	Contact Sponsor

8.4.2 BASELINE VISIT (9:00 AM \pm 1 HR, NOON \pm 1 HR, 4:00 PM \pm 1 HR)

Below is a list of study procedures to be undertaken at the Baseline Visit which must take place no more than 14 days prior to surgery and only after satisfying the medication washout (Section 8.4.1. "Washout of Hypotensive Medications" and Table 2). Conduct ocular assessments in both eyes.

[figure not shown]
Subjects meeting all criteria at the Baseline Visit will be scheduled for surgery and be randomized to a treatment arm. Randomization to treatment group will be performed using a 1:1:1 ratio and will be stratified by site. Computer-generated randomization will be administered through the electronic data capture (EDC) system with separate block randomization (block of 6) sequences for each clinical site.

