8.4.3 SURGICAL VISIT

The Surgical visit must occur no more than 45 days after the Screening visit and no more than 14 days after the Baseline visit.

Study investigators will be experienced with iStent inject implantation and will have received training on the OMNI Surgical System prior to site activation. Surgery will take place after the subject successfully completes all screening and baseline assessments and is confirmed eligible to participate in the study per inclusion / exclusion requirements.

Surgeons should follow their standard peri-operative medication regimen.

The following information will be captured at this visit:

- Surgical complications
- Number of iStent inject stents implanted (1, or 2), implantation attempts, number of injectors used, any difficulties with implantation
- Intraoperative AEs
- Perioperative medications (topical hypotensive medications administered)

8.4.4 DAY 1

1. Document changes in ocular hypotensive medications.
2. Measure IOP with Goldmann tonometer is recommended between 8:00 am and 10:00 am. Refer to Appendix A, Section 19.1.3.
3. Conduct slit lamp examination. Refer to Appendix A, Section 19.1.4 for gradingscales.
4. Record any ocular AE.
5. Schedule the subject to return for the Week 1 Visit between the recommended time frame of 8:00 am and 10:00 am.

8.4.5 WEEK 1 (DAYS 5 TO 9), MONTH 1 (DAYS 21 TO 35), MONTH 3, (DAYS 70 TO 98), MONTH 6 (DAYS 150 TO 210)

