13 PROTOCOL MODIFICATIONS AND DEVIATIONS

Protocol modifications may occur during the study. Each will be approved in writing by the sponsor before implementation. Each will undergo Ethics Committee review and approval, as necessary.

Any deviations from this protocol intended to protect the life or physical well-being of a subject in an emergency are to be reported to Sight Sciences, Inc. as well as the Ethics Committee as soon as possible, and no later than 5 working days after the emergency occurred.

All protocol deviations will be documented using the Protocol Deviation form.

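### Table 2 requires 28 days of washout for the brinzolamide/brimonidine fixed combination but at most 14 days for the same two drugs given separately

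*Combined protocol and SAP*

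**What the plan says.** Table 2 in Section 8.4.1 lists minimum washout periods by product. Three rows matter here:

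- brinzolamide alone: "Azopt® (Brinzolamide) 5 days"
- brimonidine alone: "Alphagan® (Brimonidine) 14 days"
- the two in one bottle: "Simbrinza® (Brinzolamide/Brimonidine Tartrate) 28 days"

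The table is the plan's working standard for washout. Section 8.4.1 has the Baseline visit scheduled "allowing sufficient time for complete washout of ocular hypotensive medication (refer to Table 2", and Section 8.4.2 permits that visit "only after satisfying the medication washout". The washout instruction covers both ends of the study: subjects on medication "at Screening and Month 12 will be instructed to undergo a washout". Surgery must take place "no more than 45 days after the Screening visit" (Section 8.4.3).

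The readable text gives no rule for deriving a fixed combination's period from its components. The only component-based statement is inclusion criterion 4 (Section 7.1), which counts fixed combinations by component when tallying medications at Screening.

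**The concern.** The two active drugs are the same whether they come in one bottle or two. If 14 days is enough for both when given separately, 28 days for the combination adds untreated time without adding washout. If 28 days is needed, the 14-day brimonidine row is too short. The table does not say which applies.

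What is at stake is time off treatment in glaucomatous eyes, which must show an unmedicated diurnal IOP of 22 to 36 mmHg to qualify. The plan itself treats washout as a risk: exclusion criterion 4 removes subjects for whom it is judged dangerous, and Section 8.4.1 allows a mid-washout IOP check. Because Baseline depends on meeting the Table 2 minimum, a site cannot shorten the period without a protocol deviation.

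**Working it through.** **Inputs.** All are from Table 2 unless noted. Minimum washout in days: brinzolamide 5, dorzolamide 5, brimonidine 14; timolol, travoprost, bimatoprost, latanoprost and netarsudil 28 each. Screening-to-surgery limit: 45 days (Section 8.4.3).

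**Step 1: stated period against the longest component.**

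| Fixed combination | Components (days) | Longest | Stated |
|---|---|---|---|
| Combigan | 14, 28 | 28 | 28 |
| Cosopt | 5, 28 | 28 | 28 |
| DuoTrav | 28, 28 | 28 | 28 |
| Ganfort | 28, 28 | 28 | 28 |
| Rocklatan | 28, 28 | 28 | 28 |
| Xalacom | 28, 28 | 28 | 28 |
| Krytantek | 14, 5, 28 | 28 | 28 |
| Simbrinza | 5, 14 | **14** | **28** |

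The longest-component rule reproduces seven of the eight rows. Adding the components does not explain the eighth: 5 + 14 = 19, not 28.

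**Step 2: size of the difference.** 28 − 14 = 14 days, and 28 / 14 = 2, so the required minimum is twice that of the longest component. These are minimums, so the difference in actual untreated time may be smaller.

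**Step 3: how much of the table is affected.** Named rows by class: 4 + 1 + 2 + 4 + 5 + 1 + 8 = 25. One of 25 named rows, and one of eight fixed-combination rows, is affected.

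**Step 4: who is affected at Baseline.** Only subjects taking this product without a prostaglandin analogue, beta blocker or netarsudil. Anyone on one of those already needs 28 days. The documents give no count.

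**Step 5: feasibility.** After a 28-day washout, 45 − 28 = 17 days remain before the surgery limit; after 14 days, 45 − 14 = 31 remain. Both fit. The longer period also fits the 5-to-30-day return for the Month 12 washout in Section 8.4.6.

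**Step 6: Month 12.** Section 8.6 lets only one class be reintroduced per visit and, without Medical Monitor approval, no more than one agent per visit or two-week period. This product contains two classes, an alpha agonist and a carbonic anhydrase inhibitor, which are steps 2 and 4 of the reintroduction order. The usual route back to treatment therefore leads to separate components, with 14- and 5-day minimums. The 28-day row applies at Month 12 only if a subject has nevertheless returned to the combination, for example by later consolidating the two drugs.

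**The case against.** The strongest reply is that the longest-component rule is not in the plan. A flat 28 days for every fixed combination fits all eight rows, while the longest-component rule fits seven. Simbrinza is the only row that separates the two rules, and it sides with the flat one. Table 2 also gives no reason for any of its 25 named rows, so the absence of a reason does not single this one out. This stands as far as intent goes: a reader might infer a typing error, and the table does not show one.

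The reply goes on to call the longer period cautious, since washout exists to remove the influence of medication on IOP. That does not hold on the plan's own terms. Section 8.4.1 refers to Table 2 for complete washout, and Table 2 accepts 14 days for brimonidine and 5 for brinzolamide. The extra days buy nothing that the plan says it needs.

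Several points on size do stand. Users of prostaglandin analogues, beta blockers and netarsudil face the same 28 days, so this product's users are not uniquely burdened. Exclusion criterion 4 and the optional mid-washout IOP check limit the risk. Medication is also allowed between Baseline and surgery, although that does not shorten the washout itself. The number of subjects affected is unknown and could be zero.

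A reader might also infer a bias in the primary comparison. The documents do not support that: the baseline washout is finished before randomization, and the same table applies to all three arms.

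**Conclusion.** The inconsistency is real and minor. By the plan's own standard, users of this one product with no other 28-day agent must go up to 14 days longer untreated before Baseline, with no gain in washout. A matching effect at Month 12 would be exceptional because of Section 8.6. No effect on the endpoint, the arm comparison, the sample size or the significance level is shown.

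The conclusion rests on one inference and one unknown. The inference is that two drugs given separately are washed out together once the longer minimum has passed. Table 2 does not say so, but both stated minimums are then met. The unknown is the number of affected subjects, which is probably small. Confidence is high in the mismatch itself. Whether 28 days was deliberate cannot be settled from the text.

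**What to change.** Set the brinzolamide/brimonidine row to 14 days and add one line to Table 2: a fixed combination takes the longest washout of its components. The other seven fixed-combination rows stay at 28 days under that rule. If the sponsor has a reason to keep 28 days, it should be stated, and the 14-day brimonidine row checked against it.

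The cost is a minor protocol modification under Section 13: written sponsor approval, a notice to sites and, on ethics review, "Each will undergo Ethics Committee review and approval, as necessary". If the change comes after enrolment has begun, later users of this product may have a shorter baseline washout than earlier ones, in all arms alike. It needs no additional visits or subjects.

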8.4.3 SURGICAL VISIT

The Surgical visit must occur no more than 45 days after the Screening visit and no more than 14 days after the Baseline visit.

Study investigators will be experienced with iStent inject implantation and will have received training on the OMNI Surgical System prior to site activation. Surgery will take place after the subject successfully completes all screening and baseline assessments and is confirmed eligible to participate in the study per inclusion / exclusion requirements.

Surgeons should follow their standard peri-operative medication regimen.

The following information will be captured at this visit:

- Surgical complications
- Number of iStent inject stents implanted (1, or 2), implantation attempts, number of injectors used, any difficulties with implantation
- Intraoperative AEs
- Perioperative medications (topical hypotensive medications administered)

8.4.4 DAY 1

1. Document changes in ocular hypotensive medications.
2. Measure IOP with Goldmann tonometer is recommended between 8:00 am and 10:00 am. Refer to Appendix A, Section 19.1.3.
3. Conduct slit lamp examination. Refer to Appendix A, Section 19.1.4 for gradingscales.
4. Record any ocular AE.
5. Schedule the subject to return for the Week 1 Visit between the recommended time frame of 8:00 am and 10:00 am.

8.4.5 WEEK 1 (DAYS 5 TO 9), MONTH 1 (DAYS 21 TO 35), MONTH 3, (DAYS 70 TO 98), MONTH 6 (DAYS 150 TO 210)

8.4.6 MONTH 12 (DAYS 330 TO 420)

The Month 12 visit is the final visit for any subjects that are not currently on any ocular hypotensive medications. For patients on medications, all assessments except the DIOP will be completed (listed below for 9 am), however, depending on the medications used, will return in from 5 to 30 days following medication washout for the DIOP assessment.

[figure not shown]

